3.1.1 Handling of Missing Data

No imputation for missing values will be conducted. All observed values (i.e., excluding missing values for visit) will be used for the analyses.

3.1.2 Date/Time Derived Variable Conventions

Study Day 1 (application of StrataGraft) will be considered as baseline for the endpoint calculation. If the value is not available at Study Day 1, the last available observed value prior to application of StrataGraft will be used.

3.2 Analysis Populations

All safety and efficacy analyses will be based on the mITT population.

3.2.1 Modified Intention to Treat Population

The modified intention-to-treat (mITT) population will include all subjects who enrolled and received StrataGraft.

3.2.2 Major/Minor Protocol deviation

Protocol deviation (i.e., Major, Minor) will be determined before data base lock by sponsor clinical team. The major and minor protocol deviations will be listed.

3.3 Demographics and Baseline Characteristics

Demographic characteristics, including age, age category (<65 , ≥ 65 year), sex, race, ethnicity, weight, height, BMI, baseline condition based on the Baux score and its category (<50 , ≥ 50), Modified Baux score and its category (<90 , ≥ 90), and overall TBSA burned and its category ($<\text{median}$, $\geq \text{median}$) will be summarized by all subjects on mITT population and completers which is defined as subjects complete study.

The Modified Baux score is calculated as:

Modified Baux score = age + TBSA burned + [17 x (inhalation Injury, 1 = yes, 0 = no)], where TBSA burned includes only 2nd and 3rd degree burns.

The Baux score is calculated as:

Baux score = age + TBSA burned, where TBSA burned includes only 2nd and 3rd degree burns.

The following parameters will also be summarized:

- Time of first assessment at any medical center to StrataGraft treatment, and its category (≤ 7 , >7 days)
- Time of first assessment at any medical center to assessment at this medical center (days)
- Time of burn injury date to application of StrataGraft date
- Time of burned injury date to application of StrataGraft date (≤ 7 , >7 days)
- Mean total StrataGraft (SG) treatment site area and its category ($\leq 500 \text{ cm}^2$, $>500 \text{ cm}^2$, & $\leq 1000 \text{ cm}^2$, $>1000 \text{ cm}^2$) by subject, respectively
 - SG treatment site A area and its category ($\leq 500 \text{ cm}^2$, $>500 \text{ cm}^2$)
 - SG treatment site B area and its category ($\leq 500 \text{ cm}^2$, $>500 \text{ cm}^2$)
 - SG treatment site C area and its category ($\leq 500 \text{ cm}^2$, $>500 \text{ cm}^2$)

- StrataGraft Treatment by location (Anterior trunk, Anterior Upper Extremity (upper arm + forearm), Anterior Lower Leg, Anterior Thigh, Posterior Trunk, Posterior Upper Extremity (upper arm + forearm), Posterior Lower Leg, Posterior Thigh)
- Mean total StrataGraft (SG) treatment site area and its category ($\leq 500 \text{ cm}^2$, $> 500 \text{ cm}^2$, & $\leq 1000 \text{ cm}^2$, $> 1000 \text{ cm}^2$) by treatment site regardless of their label A, B or C
- Other burn area not treated with StrataGraft (%TBSA)
- Donor site area (cm^2)

3.4 Medical History and Physical Examination

Medical history terms will be coded using the Medical Dictionary for Regulatory Activities (MedDRA), version 23.0. The frequency and percentage of subjects with medical history within each system organ class will be summarized.

The limited Physical Examination will be conducted at Screening to include evaluation of lungs, heart, abdomen, and extremities. The findings (normal, abnormal, abnormal clinical significance) of the physical examination will be recorded on the eCRF and summarized.

The acute burn history, which the subject has any relevant history associated with the subject's acute burn event, will be tabulated by body system.

3.5 Concomitant Medications

Medications will be coded using the WHODRUG dictionary (Global B3 September 2020) by using Anatomical-Therapeutic-Chemical (ATC) classification and preferred term name. ATC category (i.e., ATC 4) and Preferred term will be summarized by location (SG treatment sites, non-SG burn area, donor site, other site) and all subjects.

3.6 Concomitant Procedures

Concomitant procedure (including transfusions, use of xenograft or allogenic products, negative pressure wound therapy, etc.) will be summarized with the records throughout the duration of the study. The total number of concomitant procedure and number of subjects who had at least one concomitant procedure will be summarized by SG treatment site, non-SG burn area, not applicable and all subjects.

3.7 Treatment and Exposure

The number of subjects with 1, 2, and 3 burn sites, and numbers of StrataGraft constructs applied (per site and total per subject) will be summarized.

The observation duration from Day 1 (application of StrataGraft) to end of study will be summarized.

3.8 Efficacy and Safety Analysis

There is no hypothesis testing for the study. All analyses are descriptive.

3.8.1 Primary Endpoint Analysis

The primary endpoint of this study is:

- **Count and percentage of subjects with TEAEs.**

The TEAE is defined as those adverse events with onset date and time after the first placement of study product or those events in which the onset date and time are before the first placement of study product but worsened after the first placement of study product. To be conservative, in the case of a missing start date for an AE, the AE will be considered a TEAE. All the subjects with TEAEs will be summarized with frequency and percent in mITT population.

More analyses will be performed as described in section 3.9.1.

The subgroup analyses of TEAE will be performed as described in section 3.8.3.

3.8.2 Other Endpoint Analyses

The other endpoints of this study are:

- **Proportion of subjects with confirmed complete wound closure of all treatment sites without autograft (i.e., complete re-epithelialization without drainage and subsequently verified with confirmation assessment) on or before Week 12, supported by photodocumentation.**

Complete wound closure is defined as 100% skin re-epithelialization in absence of drainage and without autograft placement. Successful wound closure in this study requires that complete wound closure on or before Week 12 is achieved without autograft placement and is confirmed at least 14 days following the initial observation of complete closure.

The investigator will evaluate the confirmation of complete wound closure either by direct clinician observation or by subject-provided photodocumentation.

The proportion of subject with all confirmed complete treatment site closure(s) including two-sided 95% confidence intervals based on the normal approximation to the binomial will be calculated and presented.

- **Proportion of subjects with confirmed complete wound closure of all treatment sites without autograft (verified with confirmation assessment) at each visit, supported by photodocumentation.**

The planned visits are Week 1, Week 2, Week 4, Week 8, Week 12, and Week 24. However, the subjects may show up at any visit, and number and percentage will be summarized. For each visit, the denominator of the proportion of subjects is based on the total number of subjects who provided data for the visit.

- **Proportion of subjects maintaining durable wound closure by Week 24.**

Durable wound closure by Week 24 is achieved when a subject with confirmed wound closure is observed as remaining closed at least 90 days after complete wound closure through Week 24. Two summaries will be performed: 1. Denominator is mITT population 2. The denominator will be based on subjects with confirmed wound closure of all treatment sites without autograft by Week 12. The number, percentage and two-sided 95% confidence intervals based on the normal approximation to the binomial will be calculated and presented.

- **Proportion of treatment sites with confirmed complete wound closure without autograft (i.e., complete re-epithelialization without drainage and subsequently verified with confirmation assessment) on or before Week 12 and supported by photodocumentation.**

The treatment sites will be analyzed regardless of subject. Treatment site with confirmed wound closure requires treatment site complete closure on or before Week 12 is achieved without autograft placement and is confirmed at least 14 days following the initial observation of complete closure.

The investigator will evaluate the confirmation of complete treatment site closure either by direct clinician observation or by subject-provided photodocumentation.

The proportion of confirmed complete treatment site closure including two-sided 95% confidence intervals based on the normal approximation to the binomial will be calculated and presented.

- **Proportion of treatment sites maintaining durable wound closure by Week 24.**

The treatment sites will be analyzed regardless of subject.

Durable wound closure by Week 24 is achieved when a confirmed wound is observed as remaining closed at least 90 days after a confirmed complete wound closure through Week 24. Two summaries will be performed: 1. Denominator is all treatment sites 2. The denominator will be based on a confirmed treatment site wound closure by Week 12. The number, percentage and two-sided 95% confidence intervals based on the normal approximation to the binomial will be calculated and presented.

- **Time to first confirmed complete wound closure of all treatment sites in a subject without autograft (verified with confirmation assessment at least 14 days later).**

The event for Kaplan-Meier method will be the first occurrence of all confirmed complete wound closure without autograft in a subject (first observation of complete closure verified with a second observation of complete closure at least 14 days later). The time to first confirmed wound closure will be analyzed by the Kaplan-Meier estimation method. The period for this analysis is calculated as (the date of having the first confirmed event – the date of Day 1 + 1). Subjects not having any confirmed complete closure event during the study will have their time censored at the last available date in the study. Kaplan-Meier estimates by StrataGraft treatment area with confirmed wound closure will be presented for the following categories: $\leq 500 \text{ cm}^2$, $> 500 \text{ cm}^2$.

The Kaplan-Meier estimate will be computed to determine the median time to confirmed complete wound closure without autograft placement.

In addition, the event for Kaplan-Meier method will be the first occurrence of complete wound closure without grafting (which includes autograft, allograft, xenograft and other skin substitute) will also be generated.

- **Skin quality and cosmesis of treated sites assessed by POSAS scores**

The scar evaluation will use the POSAS total scores at Week 12 and Week 24. The POSAS (The Patient and Observer Scar Assessment Scale) scales are evaluated separately by clinician (observer) and subject (patient), resulting in two total scores.

Total POSAS Score of each treatment site is the sum of the scores for vascularization, pigmentation, thickness, relief, pliability and surface area scored for that treatment site, and each item is scored numerically on a ten-step scale.

Each of the individual POSAS items and the total POSAS score, represented as the mean score across all items and supported by photo-documentation, will be summarized by treatment site and overall mean score of all of the treatment sites of the subject, by clinician and subject, and for both Week 12 and Week 24.

POSAS will be summarized by clinical visit in person and remotely, respectively.

- **Number of subjects with wound-infection related events.**

Local wound infection will be determined by the clinical investigator and may include confirmatory microbiological assessment. Similarly, systemic infection will be determined by the clinical investigator and may include documentation of such signs as positive blood and/or wound cultures, fever (defined as $>38.5^{\circ}\text{C}$) and/or elevated white blood cell count.

Study treatment sites will be examined by the investigator for signs and symptoms of infection at every study visit. Cultures of the treatment sites may be obtained for microbiological evaluation at the discretion of the clinical investigator or per institutional SoC at any time during treatment. The clinical investigator will evaluate the wound culture results for clinical significance.

The wound-infection related events will be summarized by visit and SG treatment site by subject.

To evaluate the effects of initial re-grafting on SG treatment sites, initial complete wound closure with or without confirmation is not required. Grafting includes allograft, xenograft and other skin substitute, and autografting, which is separately calculated. The following endpoints evaluating the combination of initial complete wound closure, confirmation of complete closure, and grafting/autografting will be summarized by SG treatment site and overall (across all treatment sites per subject):

- Summary of subjects with re-grafting on StrataGraft treatment sites

- Proportion and 95% confidence intervals of subjects who achieved initial wound closure on or before Week 12
- Proportion of subjects who achieved initial wound closure for at least one wound site without grafting on or before Week 12
- Proportion of subjects who achieved initial wound closure for at least one wound site without autograft on or before Week 12
- Proportion of subjects who achieved initial wound closure at each visit up to Week 12
- Proportion of subjects who achieved initial wound closure without grafting at each visit up to Week 12
- Proportion of subjects who achieved initial wound closure without autograft at each visit up to Week 12
- Proportion of subjects who achieved initial wound closure with grafting at each visit up to Week 12
- Proportion of subjects who achieved initial wound closure with autograft at each visit up to Week 12
- Proportion of subjects who achieved $\geq 95\%$ wound closure without autograft at each visit up to Week 12
- Proportion of treatment sites $\geq 95\%$ wound closure without autograft at each visit up to Week 12
- Proportion and 95% confidence intervals of subjects who achieved confirmed wound closure on or before Week 12
- Proportion of subjects who achieved initial confirmed wound closure at each visit up to Week 12
- Proportion of subjects who achieved initial confirmed wound closure without grafting at each visit up to Week 12
- Proportion of subjects who achieved initial confirmed wound closure without autograft at each visit up to Week 12
- Proportion of subjects who achieved initial confirmed wound closure with grafting at each visit up to Week 12
- Proportion of subjects who achieved initial confirmed wound closure with autograft at each visit up to Week 12

- Proportion of subjects with confirmed wound closure without grafting at each visit
- Proportion of subjects with confirmed wound closure without autograft at each visit

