8.3. Concomitant Procedures

Any concomitant procedure (including transfusions, use of xenogenic or allogeneic products, negative pressure wound therapy, etc.) must be recorded in the eCRF after the consent form is signed and throughout the duration of the study.

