12.2.4. Refactoring and Delayed Wound Healing

In the event that a StrataGraft-treated area needs to be regrafted with either an autograft or a xenograft after prior treatment with StrataGraft skin tissue, the event would not be marked as an AE, but rather as a failure to close. In the event that there is an accompanying wound degradation event occurring simultaneously such as infection that results in delayed wound healing, the delayed wound healing secondary to the ongoing infection can be listed as an AE or SAE as applicable. If that infective process eventually warrants regrafting, the regrafting should still be marked as a failure to close and not an AE.

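### By-visit closure rate: a subject with a recorded autograft before closure drops out of the denominator at any later visit without data

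*SAP*

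**What the plan says.** The by-visit endpoint in SAP 3.8.2 is confirmed complete closure of all treatment sites without autograft. For it, "the denominator of the proportion of subjects is based on the total number of subjects who provided data for the visit". The SAP does not define what providing data means. It also does not say whether the by-visit result is cumulative (confirmed closure achieved by then) or status on the date. The schedule in Protocol 6.1.1 assesses both closure and continued closure.

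Protocol 12.2.4 says of regrafting a treated area, autograft included, that "the event would not be marked as an AE, but rather as a failure to close". The autograft is recorded whether or not a visit takes place. Under Protocol 8.3, concomitant procedures "must be recorded in the eCRF after the consent form is signed and throughout the duration of the study". Under SAP 3.6, the "number of subjects who had at least one concomitant procedure will be summarized by SG treatment site". SAP 3.8.2 also lists a "Summary of subjects with re-grafting on StrataGraft treatment sites".

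The list that closes SAP 3.8.2 repeats the endpoint as "Proportion of subjects with confirmed wound closure without autograft at each visit", with no denominator given. For durable closure, the same section pairs two denominators: "Two summaries will be performed: 1. Denominator is mITT population", with a second summary among subjects closed by Week 12.

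SAP 3.2 and Protocol 13.2 base efficacy analyses on the mITT population. SAP 3.1.1 and Protocol 13.3.8 rule out imputation and use observed values.

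**The concern.** Autograft before confirmed closure settles this endpoint: the subject cannot later have closure without autograft. Neither document keeps such a subject in the denominator when a later visit has no data. A failure that the database already holds can therefore vanish from the rate.

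The study has one arm and no hypothesis test, so the percentage itself is the result. If recorded failures drop out, the printed rate can exceed anything the full treated group could have. Rates at successive visits also describe different sets of subjects, so a rise over time may partly reflect who was seen.

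The no-imputation rule does not require this. It concerns missing values, and an autograft on record is an observed one. Nor does the time-to-closure analysis supply the missing figure, since "Subjects not having any confirmed complete closure event during the study will have their time censored at the last available date in the study".

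**Working it through.** The plan states no closure, autograft or missed-visit rate, so there is no figure to reproduce. The planned size of about 100 comes from SAP 2.3. All other inputs are assumptions.

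**Inputs.** N = 100 treated; n = 85 with data at a visit; x = 68 of these closed; m = 15 without data. Of those 15, a were autografted before confirmed closure and the rest are taken as unknown.

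**Formulas.**
- Rate as the SAP defines it: x/n = 68/85 = 80.0%.
- Recorded failures kept in: x/(n + a).
- Lowest possible mITT rate, all unknowns not closed: x/N = 68/100 = 68%.
- Highest possible mITT rate, all unknowns closed: (x + m − a)/N.

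| a | Reported | Failures kept | Highest possible mITT |
|---|---|---|---|
| 0 | 80.0% | 68/85 = 80.0% | 83% |
| 2 | 80.0% | 68/87 = 78.2% | 81% |
| 3 | 80.0% | 68/88 = 77.3% | 80% |
| 4 | 80.0% | 68/89 = 76.4% | 79% |
| 6 | 80.0% | 68/91 = 74.7% | 77% |
| 8 | 80.0% | 68/93 = 73.1% | 75% |
| 10 | 80.0% | 68/95 = 71.6% | 73% |

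**When the reported rate becomes unattainable.** x/n > (x + m − a)/(n + m) holds exactly when a > m(1 − x/n). Here that is a > 15 × 0.20 = 3. From 4 autografted subjects on, 80.0% lies above every value the 100 subjects could have.

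**The opposite direction.** With a = 0 and all 15 missing subjects in fact closed, the true rate is (68 + 15)/100 = 83%, above the reported 80.0%. This holds for status on the date as well as for the cumulative reading, because a closed subject who is not seen leaves both numerator and denominator. Losses can also cancel. With 75 of 100 truly closed, if 15 closed and 5 failed subjects are missing, the rate is 60/80 = 75.0%.

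**Both readings at a = 6.** Suppose 4 of the other 9 had confirmed closure earlier. Status on the date gives a range of 68% to (68 + 9)/100 = 77%. The cumulative reading gives (68 + 4)/100 = 72% to (68 + 4 + 5)/100 = 77%. The upper limit is 77% on both.

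**No missing visit data.** With m = 0 the two denominators are the same and nothing changes.

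**The case against.** The trigger is narrow. The effect needs an autografted subject with no data at the visit. One who attends already counts as not closed. Autograft is not a reason for withdrawal in Protocol 7.3. Protocol 6.1.4 has all subjects followed to the end of participation, and the list in SAP 3.8.2 tabulates closure with autograft by visit up to Week 12, so these subjects are expected to stay under assessment. Subject photographs can stand in for a missed visit, although section 10 of the Protocol does not require them when dressings may not be removed at home. Nothing shows that autografted subjects miss more visits than others. The earlier Phase 1b study (Protocol 4.3) reports closure in 27 of 28 per-protocol subjects at Month 3 and no autograft before Day 28, though with smaller treated areas (up to 440 cm², against about 2000 cm² here). All of this stands, and it limits the likely size.

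The nearest summary is also unaffected. The proportion closed on or before Week 12 is not governed by the by-visit sentence and falls under the general mITT rule of SAP 3.2, so an autografted non-closer stays in that denominator.

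Finally, the variable specifications and table shells are separate documents (SAP sections 5 and 6) and may define the phrase. They are not available here. A denominator rule still belongs in the SAP, whose stated purpose is to fix the analysis before database lock.

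**Conclusion.** The gap is real and limited. As written, the by-visit rule lets a recorded failure leave the denominator, and that component can only raise the rate. In the assumed illustration with 6 autografted among 15 missing, 80.0% is reported where keeping those failures gives 74.7% and the ceiling is 77%. The result rests on assumed attendance, closure and autograft counts, and the actual size cannot be derived from the documents.

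A reader might infer three stronger things, none of which the documents support:
- *The reported rates will be too high overall.* Missing subjects who are still closed lower the rate on either reading of the by-visit wording, so the net direction is open.
- *The Week 12 closure result is inflated.* It has its own denominator under the mITT rule. Only the descriptive by-visit profile and its repeat are affected, and the primary endpoint is untouched.
- *Missing visits must be filled in.* The argument concerns only autografts already on record. Carrying closure forward or assigning values to unseen subjects goes beyond it and sits uneasily with the no-imputation rule. The limits shown in the working serve only to gauge size.

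**What to change.** In SAP 3.8.2:

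1. Keep the observed-case table as supportive. For each visit, add a row on the mITT denominator in which a subject autografted at any treatment site before confirmed closure counts as not closed from the autograft date.
2. Print the number of subjects with unknown status at each visit. In the illustration with a = 6, the display would show 68 closed, 17 + 6 = 23 known not closed and 9 unknown. Without the last figure, 68% could be misread as a settled rate.
3. State what counts as providing data for a visit, including whether a photograph or a procedure record is enough.
4. State whether the by-visit result is cumulative or status on the date.
5. Apply the same rule to the repeated endpoint in the list that closes the section.

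The two-denominator layout already exists for durable closure. The cost is one derived status variable, extra rows per visit and a few sentences. No new data are needed. The mITT row may look less favourable than the observed-case rate.

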3 STATISTICAL METHODS AND CONVENTIONS

3.1 General Conventions

- Unless otherwise noted, the number of subjects (N), mean, standard deviation, median, minimum, and maximum will be presented for continuous variables and frequency and percentage of subjects in each category will be presented for discrete variables.
- Unless otherwise noted, confidence intervals (CIs) will be 2-sided 95% CIs.
- Listings will be sorted by subject identification, and date of the procedure or event.
- Statistical analyses will be done using Statistical Analysis Software (SAS[®]) version 9.4 or higher.
- The Kaplan-Meier estimate will be computed to determine the median time to first confirmed complete wound closure without autograft placement (date of closure is the date of the first observation of complete epithelialization without use of an autograft and confirmed with a second observation of complete closure at least 2 weeks after the first.). The 95% CI will be constructed with a generalized Brookmeyer and Crowley method.
- The Proportion and 95% CI of subjects will be calculated using the normal approximation to the binomial distribution.
- Listing will be provided for all related summary tables.

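### Durable closure needs 90 days closed through Week 24, but Week 12 to Week 24 is nominally 84 days; the second denominator has no rule for the shortfall, and the subject and site clocks are worded differently

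*SAP*

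**What the plan says.** All the rules are in SAP 3.8.2 unless stated otherwise.

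- **Success rule, subjects:** "complete wound closure on or before Week 12 is achieved without autograft placement and is confirmed at least 14 days following the initial observation".
- **Success rule, sites:** "Treatment site with confirmed wound closure requires treatment site complete closure on or before Week 12 is achieved without autograft placement and is confirmed", again at least 14 days after the first observation.
- **Durability, subjects:** "observed as remaining closed at least 90 days after complete wound closure through Week 24".
- **Durability, sites:** "remaining closed at least 90 days after a confirmed complete wound closure through Week 24".
- **Denominators:** each level has two summaries. The first uses the mITT population or all treatment sites. The second reads, for subjects, "The denominator will be based on subjects with confirmed wound closure of all treatment sites without autograft by Week 12", and for sites, "The denominator will be based on a confirmed treatment site wound closure by Week 12".
- **Date of closure:** for the Kaplan-Meier analysis, SAP 3.1 says that the "date of closure is the date of the first observation of complete epithelialization without use of an autograft and confirmed with a second observation".
- **Protocol 13.3.2:** gives one durability rule, at least 3 months after complete closure. It defines confirmed closure by determinations at two visits at least 2 weeks apart.
- **Visit windows (SAP Table 1):** ±7 days at Weeks 12 and 24, or ±14 days in a public state of emergency.

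Neither durability summary has an exclusion or a separate category for wounds with fewer than 90 days left before Week 24. SAP 3.1.1 allows no imputation.

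**The concern.** The success rules tie Week 12 to the first observed closure and let the confirmation come later. A wound first seen closed at the Week 12 visit can therefore enter the second denominator, yet on schedule it has 84 days to Week 24 against the 90 required. It would be tabulated as not durable whether or not it reopened.

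The natural use of the second denominator is to show how often a confirmed closure is maintained. As written, its complement mixes reopening with too few calendar days. The same definition carries into the durable-closure summary by burn location (SAP 3.8.3), where groups are smaller. If the different wording of the two clocks is followed literally, the subject and site figures would also rest on different start dates.

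**Working it through.** Inputs: 90 days, the 14-day confirmation interval and the Week 12 limit (SAP 3.8.2); visit windows (SAP Table 1). The plan states no figure to reproduce. Times below are days after application, so Week 12 is 84 and Week 24 is 168. In the study's numbering, where application is Day 1, each label is one higher; the differences are unchanged.

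**1. Available time from first closure at Week 12**
- Nominal: 168 − 84 = 84, which is 6 short of 90.
- ±7 days: 161 − 91 = 70 to 175 − 77 = 98.
- ±14 days (emergency only): 154 − 98 = 56 to 182 − 70 = 112.

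The protocol's 3 months does not close the gap: the shortest run of three calendar months is 28 + 31 + 30 = 89 days.

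**2. How often the windows make up 6 days**
The Week 24 visit must drift at least 6 days later than the Week 12 visit does.
- ±7 days: 9 + 8 + … + 1 = 45 of 15 × 15 = 225 date pairs (20%).
- ±14 days: 23 + 22 + … + 1 = 276 of 29 × 29 = 841 (33%).

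These counts assume equally weighted, independent visit dates. They are not expected frequencies.

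**3. The two clocks on an on-time weekly schedule**

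| First seen closed | Days to Week 24 from first closure | Days from a confirmation 14 days later |
|---|---|---|
| Week 8 | 112 | 98 |
| Week 9 | 105 | 91 |
| Week 10 | 98 | 84 |
| Week 11 | 91 | 77 |
| Week 12 | 84 | 70 |

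The latest qualifying first closure is 168 − 90 = 78 days after application on the subject clock, and 168 − 90 − 14 = 64 on the literal site clock. The subject clock affects only Week 12 first closures; the literal site clock also affects Weeks 10 and 11.

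**4. Alternative reading: confirmation itself by Week 12**
With confirmation at the Week 12 visit and first closure 14 days earlier, the subject clock gives 84 + 14 = 98 days nominally.
- ±7 days: 84 to 112, with 6 + 5 + … + 1 = 21 of 225 pairs below 90.
- ±14 days: 70 to 126, with 20 + 19 + … + 1 = 210 of 841 below 90.

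A site confirmed at Week 12, with its clock started at confirmation, still has 168 − 84 = 84 days.

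**5. Effect on the proportion**
Let E wounds have at least 90 days available and S have fewer. By definition none of the S can count as durable, so with D durable wounds the second-denominator proportion is D/(E + S) = (D/E) × E/(E + S). It can only be pulled down. Per late closer who never reopens, the loss is 1/70 = 1.4 to 1/100 = 1.0 percentage points for assumed denominators of 70 to 100. For illustration, with an assumed 80 subjects and no reopening, S of 4 to 24 (5% to 30%) caps the proportion at 76/80 = 95% to 56/80 = 70%.

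**The case against.** **The second denominator may not contain Week 12 first closures.** It is worded as confirmed closure by Week 12, and Protocol 13.3.2 makes confirmation a two-visit condition. If both visits must fall by Week 12, 225 − 21 = 204 of 225 pairs reach 90 days at subject level. This stands as an ambiguity. The success rules in SAP 3.8.2 favour the first-closure reading but do not settle it, and the site text literally fails nominally on either reading.

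**The clocks may be meant to be the same.** The date convention in SAP 3.1 and the single rule in Protocol 13.3.2 make that the likelier intent. A reader might infer that the sponsor chose a stricter clock for sites; the documents show different wording, not different intent.

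**The effect may be small.** With on-time weekly photos and the subject clock, only Week 12 first closures are exposed. But Protocol 10 expects no home photos where dressings may not be changed at home. Without photos or extra visits, the Week 12 visit collects all closures since Week 8, a 28-day rather than a 7-day interval.

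**The cause may be recoverable.** SAP 3.1 promises listings for all related summary tables, and the programming specifications and table shells are separate documents (SAP 5 and 6). Listings could allow reconstruction, but nothing in the SAP requires the split.

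**Loss to follow-up also mixes with reopening.** This is right, and the fix has to separate it too.

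**Conclusion.** The concern holds in a conditional form. Under the success rules in SAP 3.8.2, the second denominator includes wounds that usually cannot reach 90 days by Week 24 and counts them as failures of durability even if they stay closed, so the maintenance proportion is biased downward. If Week 12 limits the confirmation instead, the subject-level shortfall largely but not fully disappears, while a site confirmed at Week 12 has 84 days on the literal site clock.

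Two stronger inferences are not supported. First, not every wound first closed at Week 12 must fail: an early Week 12 visit with a late Week 24 visit can reach 90 days, and the SAP notes that "the subjects may show up at any visit". Second, the 20% and 33% are shares of date combinations, not forecasts. The documents give no distribution of closure times, so the affected share, and hence the size of the bias, is unknown.

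The arithmetic and the difference in wording are certain; the practical consequence depends on the reading and on how many wounds close late. The mITT and all-sites summaries are less affected, because there closing too late can fairly count as not achieving durability by Week 24. The endpoint is descriptive and non-primary, so no error rate is involved. It is still worth settling before database lock.

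**What to change.** In SAP 3.8.2, before database lock:

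1. Use one clock for subjects and sites: the first observed closure that is later confirmed, as in SAP 3.1 (at subject level, closure of all treatment sites). State that the Week 12 limit in the second denominator refers to that date.
2. Keep the 90-day definition and both existing summaries. For the second denominator, split the not-durable count into (a) reopened; (b) still closed at last observation but with under 90 days from first closure to the Week 24 assessment, using the scheduled date if that visit is missed; and (c) not observed to 90 days because of missed visits or loss to follow-up. Assign in that order so that each wound is counted once.
3. Beside the existing proportion, show the second-denominator proportion among those with at least 90 days of possible follow-up. Set eligibility by each subject's or site's own dates, not by outcome. A fixed cutoff of 78 days would err both ways: closure at 80 seen at 172 gives 92 days but would be dropped; closure at 77 seen at 163 gives 86 but would be kept.

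The cost is SAP wording, one derived follow-up variable and a few extra summary rows per level, with no new data. The downside is that the added proportion describes only wounds closed early enough to be followed for 90 days, so it supplements the existing one and does not replace it.
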